6.2 Appendix 2: Changes to protocol-planned analyses

The following changes to the protocol-planned analyses have been made in this SAP:

- The definition of the FAS was updated to exclude participants who did not meet key inclusion/exclusion criteria.
- Two new supplementary estimands were added for the primary endpoint, MDS-UPDRS Part I-III sum score. The population-level summaries of interest for these new estimands will be the ST de-mediated difference in target population (1) mean sum score at Month 12 and (2) mean slope over 12 months, as if the participants had not initiated ST.
- Four new supplementary estimands were added for MDS-UPDRS Part III subscale as if the participants had not initiated ST. The population-level summaries of interest for these new estimands will be the ST de-mediated difference in target population (1) mean subscale at Month 12, (2) mean subscale at Month 18, (3) mean slope over 12 months and (4) mean slope over 18 months.
- Four new supplementary estimands were added for MDS-UPDRS Part III ePD subscore as if the participants had not initiated ST. The population-level summaries of interest for these new estimands will be the ST de-mediated difference in target population (1) mean subscale at Month 12, (2) mean subscale at Month 18, (3) mean slope over 12 months and (4) mean slope over 18 months.
- ~~In the protocol, estimands for MDS-UPDRS Part I at Month 12 and Month 18 regardless of ST initiation are considered secondary estimands. In this SAP, they are considered as supplementary estimands and covered in Section 5.3.2.1.8.~~
- For the analysis of MDS-UPDRS Part II emerging symptoms, the ICE handling strategy has been updated from treatment policy to composite for ST for the main analysis, and the treatment policy approach is being proposed as a supplementary analysis.

6.3 Appendix 3: Data loss to ST initiation modelling

Data loss to ST initiation over 12 months as observed for PPMI ([Figure 6-1](#)) and assuming exponential loss for our POC study ([Figure 6-2](#)).

Figure 6-1: Observed data loss in PPMI dataset

NM

[figure not shown]
[figure not shown]

Figure 6–2: Simulated data loss in PD0053

6.4 Appendix 4: Producing summaries by treatment group and overall**Table 6-1: Treatment groups to be presented in summary tables**

	Not Randomized	Placebo	UCB0599 Arms	UCB0599 Total	All Participants
Participant disposition	X ^a	X	X		X
Protocol deviations		X	X		X
Demographics and Baseline characteristics		X	X		X
Medical history and medications		X	X		X
Adverse Events		X		X	
Other safety analyses		X	X		
IMP Compliance		X	X		
Pharmacokinetics			X		
Efficacy endpoints		X	X		

^a Only reasons for screen failure and disposition of analysis sets will include not randomized participants.

Note: This table is a guide, the study TFL shells should be followed for which groups to display for each individual output.

6.5 **Appendix 5: MDS-UPDRS Part I-III sum score, MDS-UPDRS Part III subscale and ePD subscore: imputation, ST de-mediation and modelling**

This Appendix describes in detail the approaches and workflow to be implemented by the UCB statistical/statistical programming team to produce additional (CSR-ready) TFLs for the Month 18 delivery.

6.5.1 **Overview of Estimands and General Approach**

Estimands

The treatment differences of interest will be:

- Minzasolmin 360mg/day vs Placebo,
- Minzasolmin 180mg/day vs Placebo.

The approaches described below concerns the production of TFLs regarding the following 5 estimands based on 3 MDS-UPDRS based endpoints:

- Symptomatic Treatment (ST) de-mediated difference in MDS-UPDRS Part I-III sum score mean point estimate at Month 12 ([section 5.3.1.4.1](#));
- ST de-mediated difference in MDS-UPDRS Part III subscale mean point estimate at Month 12 ([section 5.3.2.1.4](#));
- ST de-mediated difference in MDS-UPDRS Part III subscale mean point estimate at Month 18 ([section 5.3.2.1.4](#));
- ST de-mediated difference in MDS-UPDRS Part III ePD subscore mean point estimate at Month 12 ([section 5.3.2.1.4](#));
- ST de-mediated difference in MDS-UPDRS Part III ePD subscore mean point estimate at Month 18 ([section 5.3.2.1.4](#))

Five supplementary estimands based on the slope for these 3 endpoints will also be implemented:

- ST de-mediated difference in MDS-UPDRS Part I-III sum score mean slope over 12 months ([section 5.3.1.4.3](#));
- ST de-mediated difference in MDS-UPDRS Part III subscale mean slope over 12 months ([section 5.3.2.1.4](#));
- ST de-mediated difference in MDS-UPDRS Part III subscale mean slope over 18 months ([section 5.3.2.1.4](#));
- ST de-mediated difference in MDS-UPDRS Part III ePD subscore mean slope over 12 months ([section 5.3.2.1.4](#));
- ST de-mediated difference in MDS-UPDRS Part III ePD subscore mean slope over 18 months ([section 5.3.2.1.4](#)).

Methodological Approach

ST de-mediation of randomized treatment, to estimate the direct effect of the interventional UCB0599 treatment on the outcome compared to the reference (Placebo) treatment, will be achieved by implementation of a g-estimation approach, which is based on a linear structural nested mean model (SNMM, Vansteelandt & Joffe, 2014).

On implementing the g-estimation, a vector of (MDS-UPDRS) outcomes that would have been seen if no ST had been given is obtained, and the effect of the randomized treatment can be obtained from this vector of ST de-mediated outcomes, by fitting mixed effect models (MEMs) to compare the mean at a given time point (Month 12 or 18), or the slope over a period of time (12 or 18 months) between randomized arms.

Importantly, the standard error for the point estimates must be corrected for the fact that the final analysis model is run on ‘predicted’ outcomes, i.e. ‘predicted’ from the SNMMs (case of uncongeniality to the analysis model), which carry uncertainty in the estimated effect of ST. This will be achieved by using a non-parametric bootstrapping approach.

In addition, implementation of the g-estimation requires that the missing data be imputed *a priori*. Intermittent missing data will be imputed assuming missing at random (MAR). Longitudinal/monotone missing data from participants who discontinued the study for reasons unrelated to randomized treatment or who are lost to follow-up (due to unknown reasons by definition) will be imputed assuming MAR, while longitudinal/monotone missing data from participants who discontinued the study for reasons related to randomized treatment (i.e. due to lack of efficacy) will be imputed assuming missing not at random (MNAR), using a relatively simple Reference-Based Imputation approach (RBI), i.e. control-based pattern imputation. As the 3 endpoints of interest are continuous, we will adopt multiple imputation (MI) approaches.

The application of reference-based imputation (RBI) for some of the MNAR data also represents a case of uncongeniality to the analysis model: the imputation model is uncongenial with the analysis model (Bartlett & Hughes, 2020). Therefore, to obtain adequate estimates of standard errors for the point estimates of interest, the recommended approach is to first bootstrap the trial data, then impute via MI. In our case, we will adopt the so-called MI Boot Percentile approach as implemented by (section 3.2.1 in Bartlett & Hughes, 2020), where first $B = 200$ bootstrap samples of the data are generated, then $M = 10$ imputations of each B bootstrap sample are generated to obtain $B \times M$ datasets for each endpoint. G-estimation models are then applied to each of the $B \times M$ dataset, followed by the analysis model(s) and the relevant parameters mean and corresponding (robust) 95% bootstrap percentile-CI are then obtained through the approach outlined below. Note that to be conservative, RBI data from participants who discontinued the study for reasons related to randomized treatment will not be ST de-mediated.

Schematic of the Methodological Approach

1. Bootstrap observed data B times, by randomized treatment group (described in [Section 6.5.3](#))
2. For each B bootstrap sample, use MI to impute missing data M times, according to MAR or MNAR paradigms (described in [Section 6.5.4](#))
3. Apply g-estimation once to each $B \times M$ dataset (described in [section 6.5.5](#)), excluding participants who discontinued the study for reasons related to randomized treatment
4. Apply analysis model to each ST de-mediated $B \times M$ dataset (detailed in [section 6.5.6](#))
5. Obtain dataset-specific mean point estimate and corresponding 95% CI based on bootstrap percentiles over all $B \times M$ datasets (detailed in [section 6.5.7](#)).

6.5.2 Data Pre-processing

Participant selection

See details in [section 6.6](#).

Endpoint datasets

Create 3 separate datasets for the 3 endpoints

- MDS-UPDRS Part I-III sum score from baseline to Month 18;
- MDS-UPDRS Part III subscale from baseline to Month 18;
- MDS-UPDRS Part III ePD subscore from baseline to Month 18.

If a particular subscale (Part I, II or III) is missing at baseline, then the corresponding data from any available visit prior to randomization will be used instead, i.e. most often data collected at the screening visit ([section 5.1.2.1.5](#)). Participants with missing baseline data for a particular endpoint will be excluded from the corresponding dataset ([section 4](#)).

A description of the items which are part of the MDS-UPDRS Part III subscale are presented in [Table 6.2](#). All items are originally scored on a 5-point Likert scale: '0: No problems', '1: Slight', '2: Mild', '3: Moderate', and '4: Severe'. The ePD subscore selected is the 15-item set, which contains all 5 Rigidity items (3.3), Finger tapping (3.4, Right/Left), Hand movements (3.5, Right/Left), Pronation-supination of the hands (3.6, Right/Left), Toe tapping (3.7, Right/Left), and Leg agility (3.8, Right/Left). The ePD subscore will be constructed by summing the score for the 15 items.

Table 6-2: Items to be included in the 15-item MDS-UPDRS Part III ePD subscore

Item	Description	15-item set
3.1	Speech	
3.2	Facial expression	
3.3	Rigidity in the joints	
	Neck	
	Upper joints/extremities (Right/Left)	
	Lower joints/extremities (Right/Left)	
3.4	Finger tapping (Right/Left)	
3.5	Hand movements (Right/Left)	
3.6	Pronation-supination movements of hands (Right/Left)	
3.7	Toe tapping (Right/Left)	
3.8	Leg agility (Right/Left)	
3.9	Arising from chair	
3.10	Gait	
3.11	Freezing of gait	
3.12	Postural stability	
3.13	Posture	
3.14	Global spontaneity of movement	

Table 6–2: Items to be included in the 15-item MDS-UPDRS Part III ePD subscore

Item	Description	15-item set
3.15	Postural tremor (amplitude) of the hands (Right/Left)	
3.16	Kinetic tremor (amplitude) of the hands (Right/Left)	
3.17	Rest tremor amplitude	
	Lip/Jaw	
	Upper limb/extremity (Right/Left)	
	Lower limb/extremity (Right/Left)	
3.18	Constancy of rest tremor	

Steps described in [sections 6.5.3](#) to [6.5.7](#) below will be performed for each of the 3 datasets separately.

For all relevant procedures, the seed will be set to **2024**, at the level of the SAS procedure statement.

Validation/QC approaches are detailed in section 6.5.8.

6.5.3 Bootstrapping

- Prior to bootstrapping and in preparation for imputation of longitudinal/monotone missing data (see [section 6.5.4](#)), participants will be classified as having monotonic missing data either for reason not related to randomized treatment, or for reasons related to randomized treatment. Participants who discontinued randomized treatment for lack of efficacy prior to study termination or loss-to-follow-up will be included in the latter case.
- Sampling with replacement of each endpoint dataset
- Balanced sampling: sample for each randomized treatment arm separately (STRATA statement)
- Bootstrap **B = 200** times (using **B** as specified in the so-called MI Boot Percentile approach implemented by Bartlett & Hughes, 2020 section 3.2.1)
- Bootstrap using SAS PROC SURVEYSELECT procedure with options METHOD=URS, OUTHITS and SAMPRATE=1.

6.5.4 Handling of Missing Data

Intermittent missing data, i.e., missing values for a given subject that has available data before and after the missing time point, will always be assumed to be MAR.

Longitudinal/monotone missing data, i.e., where all subject data is missing after a given time point, can fall into 2 categories, MAR or MNAR (also refer to [section 6.5.3](#)).

Briefly, longitudinal/monotone missing data from participants who discontinued the study for reasons unrelated to randomized treatment or who are lost to follow-up (due to unknown reasons by definition) will be imputed assuming MAR; longitudinal/monotone missing data from participants who discontinued the study for reasons related to randomized treatment (i.e. due to

lack of efficacy) will be imputed assuming missing MNAR, using RBI, here control-based pattern imputation (LingLing, 2019).

Imputation will be applied separately to each **B** bootstrap data samples. A set of **M = 10** imputations per bootstrap data sample will be generated.

For all imputation approaches, time will be set to planned (rather than actual) visit time, i.e. 0, 2, 4, 6, 8, 10, 12, 14, 16 and 18 months, as actual visit time since baseline visit cannot be derived for participants with missing longitudinal/monotone data. Month 18 visit will be set as reference.

Imputation of intermittent MAR data will be implemented using multiple imputation (MI) via Markov Chain Monte Carlo (MCMC) and applying monotone regression (MI-MCMC using the SAS PROC MI procedure with methods/statements MCMC, VAR, with options IMPUTE = monotone and CHAIN = multiple).

Imputation of longitudinal/monotone MAR data will be implemented using MI-MCMC and applying monotone regression (SAS PROC MI procedure with methods/statements MCMC, VAR and MONOTONE REG)

Imputation of longitudinal/monotone MNAR data will be implemented using MI-MCMC, and applying monotone regression but specifying that only observations collected under placebo are to be used to derive the imputation, i.e. RBI (SAS PROC MI procedure with methods/statements MONOTONE REG and MNAR = model).

- For each **B** bootstrap sample, subsets will be created according to each randomized treatment arm, i.e. 3 subsets.
 - Symptomatic treatment (ST) status will be ignored to avoid creating groups with too low sample size for reliable MI.
- MI will be applied to each bootstrap sample subsets separately.
- For each **B x 3** bootstrap sample subset:
 - And for ALL participants, the intermittent missing values will be filled in using the MI-MCMC method, with a total of **M=10** sets of imputations being performed, using data from the same randomized treatment arm subset;
 - For participants randomized to active treatment with monotone MAR data or participants randomized to Placebo, missing data will be imputed by applying monotone regression on these 10 intermittent missing-imputed subsets, using data from the same randomized treatment arm subset;
For participants randomized to active treatment with monotone MNAR data, missing data will be imputed by applying monotone regression on these 10 intermittent missing-imputed subsets, using data from the randomized placebo arm subset. If any issues are encountered using the monotone MI assuming MNAR approach, a monotone MI assuming MAR approach will be used instead.

Imputed dataset from participants with monotone MAR and MNAR data will be stacked back together to reconstitute the full list of trial participants for each imputed set.

- For each **B** bootstrap sample, the **M**-imputed randomized treatment arm subsets will be stacked again into **M** complete imputed datasets corresponding to a single bootstrap sample (full trial).
- If values outside of the pre-defined range of values for MDS-UPDRS endpoints (defined as the minimum and maximum values which could be observed) are imputed, they will be reset to the relevant lower or upper limit of the range after completion of the MI procedure
 - MDS-UPDRS Part I-III sum score: 0 – 236
 - MDS-UPDRS Part III subscale: 0 – 132
 - MDS-UPDRS Part III subscore: 0 – 60
 - MDS-UPDRS Part II subscale: 0 – 52
 - MDS-UPDRS Part I subscale: 0 – 52

At the end of the imputation process, **B x M** complete datasets will be available.

For all imputation models, sex (reference = Male), age at informed consent signing (agegrp4, reference = 60-69), and geographic region (reference = Europe) will be included as baseline demographics. No missing data is expected for baseline demographics. MI models will only allow continuous variables. Therefore, categorical variables will be re-coded as indicator variables as follows:

Baseline demographics (included in all analyses)

- For sex: Male = 0, Female = 1
- For age at informed consent: 60-69 = 0, 40-49 = 1, 50-59 = 2, 70+ = 3
- For geographic region: Europe = 0, North America = 1

Baseline/screening data for time varying covariates MDS-UPDRS Part II and DaT-SPECT Striatum SBR (not mean-centered, constrained to be positive) will also be included as baseline covariates. Where missing data are present, a MI-MCMC approach assuming MAR – as for intermittent missing data – will be used. For all variables, imputed datapoint outside the expected range for the variable will be rest to the appropriate lower/upper limit of the range.

Exploratory sensitivity analyses may be run with using additional covariates for the imputation step (details to be included in the exploratory analysis plan).

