### Estimator

Monotone missing data from participants who dropped out of the study will be imputed using RBI and according to ST intake status.

Imputed datasets for those dropouts will be summarized into a single dataset to obtain Month 18 estimates, which will then be combined with the de-mediated Month 18 estimates.

An ANCOVA will be applied to the complete Month 18 data. Treatment will be included in the model as a categorical fixed effect, gender, age at Baseline, and Baseline MDS-UPDRS Part III subscale (ePD subscore) data will be fitted as covariates.

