1.2.6 Study termination and loss to follow-up

A participant may withdraw from the study at any time at his/her own request or may be withdrawn at any time at the discretion of the Investigator for safety, behavioral, IMP compliance, or administrative reasons. If a study participant withdraws or is withdrawn, he or she should be encouraged to perform the End-of-Treatment (EOT) Visit and the Safety Follow up Visit approximately 30 days after last dose of IMP.

Study termination will only be considered treatment-related if the reason for termination is 'lack of efficacy'. As a default approach, MAR will be assumed and the implicit imputation of likelihood-based linear models (for gaussian distributed outcomes), will be applied to any occurrence of study termination (including treatment-related termination) and the event will be ignored. For event-based outcomes, the approach will depend on whether the termination is considered to be treatment-related or not. For treatment-related termination, imputation assuming non-response to treatment will be applied (for example, for time to ST initiation we would impute treatment-related termination as a progression-related 'event'). For other causes of study termination (including loss to follow-up) data will be considered right censored at the time of termination (and ignored).

In well-designed clinical studies it is reasonable to assume that dropout patterns follow the MAR mechanism, although missing not at random (MNAR) data cannot be ruled out (Liu-Seifert, 2015). As an alternative approach, a different hypothetical strategy, such as a reference-based imputation (RBI) approach (for gaussian distributed outcomes) will be used when participants terminate the study for treatment-related reasons for MDS-UPDRS-based continuous endpoints estimands (Appendix 5).

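### SAP 6.5.4 lets own-arm MAR replace placebo-based imputation of active-arm lack-of-efficacy exits on an undefined trigger; the effect is small and conditional, and a placebo-only fallback would avoid it

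*SAP*

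**What the plan says.** SAP Appendix 5 (6.5.1 and 6.5.4) splits monotone missing data by reason for leaving. Those who leave for reasons unrelated to treatment, and those "who are lost to follow-up (due to unknown reasons by definition) will be imputed assuming MAR", are imputed from their own arm. Treatment-related leavers are classed as MNAR. SAP 1.2.6 defines that class narrowly ("Study termination will only be considered treatment-related if the reason for termination is" lack of efficacy), and 6.5.3 adds people who stopped study drug for that reason before leaving.

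For the MNAR class, 6.5.4 says: "For participants randomized to active treatment with monotone MNAR data, missing data will be imputed by applying monotone regression", and does so "using data from the randomized placebo arm subset". The next sentence is the fallback: "If any issues are encountered using the monotone MI assuming MNAR approach, a monotone MI assuming MAR approach will be used instead". The SAP does not say what counts as an issue, who decides, whether the switch applies to one bootstrap sample or to a whole endpoint, or how its use is reported.

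The protocol's estimator for the de-mediated Part III and ePD estimands (9.3.1.1.3 for Month 12, 9.3.1.2.3.1 for Month 18) has no such fallback: "Monotone missing data from participants who dropped out of the study will be imputed using RBI and according to ST intake status". It covers all dropouts. SAP 6.2 (Appendix 2, changes to protocol-planned analyses) lists neither the narrowing to lack-of-efficacy exits nor the fallback.

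**The concern.** Lack-of-efficacy leavers in the active arms are the only people who still receive reference-based imputation in Appendix 5. If the fallback is used, none remains. These participants are then imputed as if they went on progressing at the active arm's rate, although the SAP classes their data as MNAR. When the active arm does better than placebo, that gives them a lower imputed score than the placebo-based rule would.

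The analyses affected matter. The ePD difference at Month 12 is a key secondary estimand in both documents, and de-mediation was added because more participants than expected started symptomatic treatment (ST). The sponsor runs these analyses in-house (SAP 5.1), and on real data the placebo-based step needs the treatment codes. A change of missing-data assumption should therefore not depend on a judgement made at that stage.

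**Working it through.** **The plan's own figure.** SAP 3.1 and Table 3-1 give intercept variance 154.0, slope variance 0.43, residual variance 31.1, Z = 2.56 and N1·Var(T) = 85.57. SAP 3.2 gives an effect of 0.27 points/month. With σ² = 154.0 + 31.1 = 185.1:

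n = 2 × [(1 − 154/185.1) + (0.43/185.1) × 85.57] × 2.56² / (85.57 × 0.27²/185.1) = 142.66, rounded up to the stated 143 per arm. The inputs are therefore read correctly.

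**Shift per participant.** Let h be the visit times observed before exit, T the target visit and δ the monthly benefit. Let B be the regression coefficients of the score at T on the scores at h, under the variances above. Own-arm imputation carries the full benefit δT. Placebo-based imputation carries only the part predicted from the observed history, δ·(B·h). So

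gap = δ × (T − B·h).

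- *Sum score, Month 12, exit after Month 6* (h = 0, 2, 4, 6). B = (−0.0397, 0.1548, 0.3492, 0.5437). B·h = 2(0.1548) + 4(0.3492) + 6(0.5437) = 4.97. Gap = 0.27 × (12 − 4.97) = **1.90 points**.
- *Part III, Month 18, exit after Month 6*. δ = 0.19 (SAP 3.3). No Part III variances are given, so the sum-score ones stand in. B = (−0.2218, 0.1002, 0.4222, 0.7442). B·h = 6.35. Gap = 0.19 × (18 − 6.35) = **2.21 points**.

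An intercept-slope correlation of 0.43 (the value reported in SAP 3.1) changes either figure by less than 0.1. A cruder reckoning, which counts only the benefit after exit, gives 0.27 × 6 = 1.62 for the first case.

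**Shift in the treatment difference.** Multiply by the share q of the active arm in this class. The documents do not give q. SAP 3.2 plans 10% study termination by Month 12 from all causes. I assume 5%, with a range of 3% to 10%.

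| Estimand | q = 3% | q = 5% | q = 10% |
|---|---|---|---|
| Sum score, Month 12 (1.90) | 0.06 | 0.09 | 0.19 |
| Part III, Month 18 (2.21) | 0.07 | 0.11 | 0.22 |

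Against the planned 12-month sum-score effect of 12 × 0.27 = 3.24, the first row is about 2% to 6% (3% at q = 5%). The standard error implied by the design is 3.24/2.56 = 1.27, so 0.09 is about 7% of one standard error.

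**Direction.** This was checked by simulation with 200,000 per arm, the same variance components, ideal de-mediation, ST use of 20% or 58%, and assumed ST effects of 0, 4 or 8 points. About 7% to 9.5% of the active arm left for lack of efficacy. Entries are the change in the Month 12 difference when MAR replaces placebo-based imputation (negative favours the drug).

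| Case | Change |
|---|---|
| Planned benefit, leavers kept out of de-mediation | −0.14 to −0.18 |
| No true effect, leavers kept out | about 0.00 |
| Active worse than placebo, leavers kept out | +0.13 to +0.19 |
| Planned benefit, leavers on ST at exit and de-mediated | +0.14 to +0.54 |

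The last row is open because the SAP is not consistent. The schematic in 6.5.1 excludes these participants from g-estimation by reason for leaving. The note in 6.5.5 words the exclusion for reference-imputed data, which would no longer exist after the switch.

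**The case against.** Much of the case for leaving the text alone is sound. MAR is the SAP's general default for study termination, treatment-related termination included (1.2.6), and the primary analysis already uses it for these people. The trial is exploratory, has no multiplicity control, and warns against over-reading p-values (SAP 2). The narrowing from all dropouts to lack-of-efficacy exits comes from the SAP's main rule, not from the fallback, and protocol 9.5 sends imputation detail to the SAP. All of this limits the importance of the point. It does not remove it: 1.2.6 also commits to reference-based imputation for treatment-related exits in the Appendix 5 endpoints, and the fallback withdraws that commitment on an open condition.

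A reader might infer more than the documents support:

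- *That the placebo-based model cannot be run as written*, because 6.5.4 also says "MI will be applied to each bootstrap sample subsets separately" and an active-arm subset has no placebo rows. The specific instruction to use the placebo subset answers this. The wording is loose; it does not describe an impossible step.
- *That the fallback always favours the drug, or inflates type I error.* It does neither. The shift is about zero with no true effect, goes against the drug if active is worse, and can reverse if these participants are de-mediated.
- *That a Month 18 sum-score shift is at stake.* The de-mediated sum score is analysed to Month 12 only (5.3.1.4.1, 6.5.1). Month 18 applies to Part III and ePD.
- *That MNAR and MAR results would be mixed across the 2,000 datasets in one interval.* The SAP does not plan this. It only fails to say at what level the switch would operate.

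**Conclusion.** The point holds as a cheap improvement. On an undefined trigger, SAP 6.5.4 can replace the one remaining placebo-based imputation with an assumption that the SAP does not adopt for these participants in Appendix 5, and that the protocol's estimator for the Part III and ePD estimands does not provide for. If active progresses more slowly than placebo and these participants remain outside de-mediation, the estimate moves toward the drug by an amount that is small next to the planned effect and its standard error.

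The size rests on an assumed share of lack-of-efficacy exits, exit at Month 6, the planning effects, and sum-score variances as a proxy for Part III. The documents give no Month 18 target for Part III, so I do not express that shift as a percentage. The primary mixed model is untouched.

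**What to change.** Replace the fallback sentence in SAP 6.5.4 with text such as:

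> For each bootstrap sample and imputation, active-arm participants with MNAR monotone data are imputed from monotone regressions whose coefficients are estimated from placebo participants only (active rows are imputed but do not enter the fit). If a model fails, a reduced placebo-only model with fewer baseline covariates is used for that endpoint in all bootstrap samples. Own-arm MAR is not used for these participants, and they stay excluded from ST de-mediation whichever model is used.

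The clause on active rows is needed. Simply appending these participants to the placebo subset would let their observed visits enter the regression, against the SAP's own condition "specifying that only observations collected under placebo are to be used to derive the imputation". Applying one model to all bootstrap samples keeps a single assumption behind each percentile interval, and the last clause settles the inconsistency between 6.5.1 and 6.5.5.

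Also list in SAP Appendix 2 that reference-based imputation is narrower than in protocol 9.3.1.1.3 and 9.3.1.2.3.1.

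The cost is a few sentences and a data-step change in the program. The estimate may come out slightly less favourable to the drug.
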